4.0 Recruitment Methods

4.1 Identification of subjects

Patients are normally scheduled for ultrasound guided injections as part of their normal care following referral. A member of the research team will review the schedules of the physician investigators who provide these injections to identify patients scheduled for ultrasound guided glenohumeral joint injections and pre-screen for eligibility.

4.2 Recruitment process

Potential candidates may be contacted via telephone prior to the scheduled appointment to determine interest in the study. If a patient expresses interest in the study a member of the research team will meet with the patient at their scheduled clinic appointment and informed consent will be obtained. If a potential patient is unable to be reached prior to the scheduled appointment, the study opportunity will be presented to the patient at the time of the clinic appointment.

4.3 Recruitment materials

Phone Script

4.4 Eligibility/screening of subjects

The clinic schedules of the investigators performing the injections will be reviewed to identify potential patients. A review of the medical record for inclusion and exclusion criteria will be completed to determine eligibility. This study is asking for waiver of authorization for the use of PHI to pre-screen potential subjects for eligibility.

5.0 Consent Process and Documentation

5.1 Consent Process

5.1.1 Obtaining Informed Consent

5.1.1.1 Timing and Location of Consent

- After the potential subject express interest in participating, the formal written consent process will occur. Written consent will occur on the day of the scheduled outpatient clinic visit for the ultrasound guided injection.

5.1.1.2 Coercion or Undue Influence during Consent

- Subjects will be given ample time to read and review the consent form on their own and ask any questions they may have. The researcher obtaining consent will review the consent form in entirety and will clearly indicate that participation is voluntary. The consent process will occur in a private setting and will be administered by a member of the research team who is not the treating physician. Consent will be obtained in accordance with principles of GCP and ICH guidelines.

5.1.2 Waiver or alteration of the informed consent requirement

Requested for the purpose of pre-screening medical records and patients schedules for eligibility.

5.2 Consent Documentation

5.2.1 Written Documentation of Consent

A member of the research team will assist in the explanation and obtaining written consent. A copy of the signed consent will be given to the patient and a copy will be placed in the medical record.

5.2.2 Waiver of Documentation of Consent (Implied consent, Verbal consent, etc.)

Not Applicable

5.3 Consent – Other Considerations

5.3.1 Non-English Speaking Subjects

Not Applicable

5.3.2 Cognitively Impaired Adults

5.3.2.1 Capability of Providing Consent

Not Applicable

5.3.2.2 Adults Unable To Consent

Not Applicable

5.3.2.3 Assent of Adults Unable to Consent

Not Applicable

5.3.3 Subjects who are not yet adults (infants, children, teenagers)

5.3.3.1 Parental Permission

Not Applicable

5.3.3.2 Assent of subjects who are not yet adults

Not Applicable

6.0 HIPAA Research Authorization and/or Waiver or Alteration of Authorization

6.1 Authorization and/or Waiver or Alteration of Authorization for the Uses and Disclosures of PHI

Check all that apply:

- Not applicable, no identifiable protected health information (PHI) is accessed, used or disclosed in this study. [Mark all parts of sections 6.2 and 6.3 as not applicable]
- Authorization will be obtained and documented as part of the consent process. [If this is the only box checked, mark sections 6.2 and 6.3 as not applicable]
- Partial waiver is requested for recruitment purposes only (Check this box if patients' medical records will be accessed to determine eligibility before consent/authorization has been obtained). [Complete all parts of sections 6.2 and 6.3]
- Full waiver is requested for entire research study (e.g., medical record review studies). [Complete all parts of sections 6.2 and 6.3]
- Alteration is requested to waive requirement for written documentation of authorization (verbal authorization will be obtained). [Complete all parts of sections 6.2 and 6.3]

6.2 Waiver or Alteration of Authorization for the Uses and Disclosures of PHI

6.2.1 Access, use or disclosure of PHI representing no more than a minimal risk to the privacy of the individual

6.2.1.1 Plan to protect PHI from improper use or disclosure

Information is included in the "Confidentiality, Privacy and Data Management" section of this protocol.

6.2.1.2 Plan to destroy identifiers or a justification for retaining identifiers

All SPADI data will be entered into Redcap with each patient receiving a patient identifier prior to being entered. All paper copies will be destroyed at the completion of the study and will be stored in the locked office of the research coordinator until that time.

6.2.2 Explanation for why the research could not practically be conducted without access to and use of PHI

PHI is needed for identification of patients and determination of eligibility. A unique study code number will be used for identification of study data. The linking list will be destroyed upon completion of the study.

6.2.3 Explanation for why the research could not practically be conducted without the waiver or alteration of authorization

The study team would be unable to identify the appropriate patients to be included in this research study.

6.3 Waiver or alteration of authorization statements of agreement

Protected health information obtained as part of this research will not be reused or disclosed to any other person or entity, except as required by law, for authorized oversight of the research study, or for other permitted uses and disclosures according to federal regulations.

The research team will collect only information essential to the study and in accord with the 'Minimum Necessary' standard (information reasonably necessary to accomplish the objectives of the research) per federal regulations.

Access to the information will be limited, to the greatest extent possible, within the research team. All disclosures or releases of identifiable information granted under this waiver will be accounted for and documented.

7.0 Study Design and Procedures

7.1 Study Design

This is a prospective, randomized, three-arm, double-blind clinical trial comparing steroid concentrations in patients undergoing intraarticular glenohumeral joint injections.

7.2 Study Procedures

7.2.1 Pre-Clinic appointment

- A member of the research team will review the weekly clinic schedules of the contributing physicians to identify patients scheduled for a glenohumeral joint ultrasound guided injection. Patients will be pre-screened for eligibility by reviewing the medical record. The patients will need to meet the inclusion criteria with radiographic evidence of glenohumeral OA within the last year, 18 years or older, and will have already been evaluated by the referring physician and a clinical diagnosis established due to symptoms that will include pain attributed to glenohumeral osteoarthritis, pain with range of motion, and/or functional limitations longer than 3 months. The medical record will also be reviewed for exclusion criteria including previous guided steroid injection of the glenohumeral joint within 3 months, previous diagnosis of inflammatory arthritis, rotator cuff tear, or immunocompromised. Finally a previous shoulder surgery and allergy to steroid or lidocaine will exclude the patient. Patients meeting pre-screening criteria will be contacted via phone call and presented with the study opportunity. Patients will be asked a series of questions to assess eligibility based on whether they are English speaking and if they are able to provide informed consent. For patients expressing interest in the study, arrangements will be made for a member of the research team to meet with the patient at their scheduled clinic appointment where the full consent discussion will occur.
- Potential patients who were unable to be reached prior to their scheduled clinic visit will be met with by a member of the research team at the time of the clinic appointment and presented with the study opportunity. Patients expressing interest in the study will be assessed for eligibility based on the inclusion exclusion criteria and informed consent will be obtained.

Once it has been determined that the patient is interested in participation and has met all inclusion/exclusion criteria thus far there will be one final step in assessing eligibility. The patient will be excluded if they have a Kellgren and Lawrence classification of 1 or less on radiograph. In order to make this assessment the research coordinator will contact our musculoskeletal radiologist who is a contributor to this project. They will then review the radiographs of the patient to make this assessment. If the patient meets the radiographic criteria they will be deemed eligible for the study.

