2.0 Background

2.1 Scientific Background and Gaps

Osteoarthritis (OA) affects 54.4 million US adults and 23.7 million (43.5%) have arthritis-attributable activity limitation¹. As the condition progresses, pain and functional disability increase. Patients usually begin treatment with conservative measures including physical therapy and administration of nonsteroidal anti-inflammatory drugs before obtaining a corticosteroid injection². Corticosteroid injections have a patient-specific duration that often provide relief for a month before the effects begin to taper with most individuals returning to baseline by 2-3 months post injection^{3,4}.

Unfortunately, data on intraarticular injections is not robust and primarily focused on hip, knee, and disease processes rather than the glenohumeral joint⁶⁻⁸. For example, steroid concentrations have been studied in adhesive capsulitis, where 20 and 40mg of triamcinolone acetonide were used with no statistical significance between the two⁶. When a placebo was added, both doses were better than the placebo, but once again no difference was seen between the two steroid concentrations⁷. Another study, looking at knee osteoarthritis, found that high dose steroids had a larger effect on duration⁸, but other studies have shown no difference in duration between the 40mg and 80mg concentration of triamcinolone acetonide⁹.

Intraarticular injections do have adverse effects. Similar to steroids taken orally or intravenously, intraarticular injections have a similar side effect profile. Fortunately, intraarticular injections are localized, by the nature of the procedure, and the chances of experiencing a significant side effect is rare^{10,11}. The most common side effects are steroid flare, allergic reaction, facial erythema, hypo- pigmentation, fat pad necrosis, cutaneous atrophy, and a transient increase in blood glucose¹¹. Some of the rare side effects have been seen in case reports include idiopathic central serous chorioretinopathy, decrease in breast milk production, sepsis, tendon rupture, and cataracts¹¹. In addition, the administration of steroid injections are limited to being done every three months due to risk of weakening tendons, and acceleration of cartilage loss^{11,12}.

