3.2 Exclusion Criteria

- Previous guided steroid injection of the glenohumeral joint within 3 months
- Previous diagnosis of inflammatory arthritis, rotator cuff tear, or immunocompromised
- Previous shoulder surgery
- Allergy to steroid or lidocaine
- A Kellgren and Lawrence classification of 1 or less on radiograph
- Non-English Speaking
- Inability to provide informed consent

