7.2.2 Clinic appointment

A member of the research team will meet with the patient. The consent will be read and reviewed with the patient. After obtaining informed consent, the patient will be asked to complete the SPADI. This will be completed on paper and entered in to the REDCap database by a member of the research team. Patients will be asked questions regarding nicotine use, pain relievers use 24 hours prior to the injection, recent therapies for shoulder pain, and dominant arm. This data will be recorded in the research records. The coordinator will randomize the patient. The patient will be randomized into one of three study arms 1) 20 mg Triamcinolone with 3 cc of 1% Lidocaine, 2) 40 mg Triamcinolone with 3cc of 1% Lidocaine, or 3) 80mg Triamcinolone with 3cc of 1% Lidocaine. The injection will be prepared by a non-blinded investigator based on the study arm selected following standard of care protocols. Standard clinic protocol involves applying a patient label to the syringe. To assist with the blinding process, an additional label will be applied to the body of the syringe to ensure the volume of the syringe cannot be determined.

For the actual injection we will be using patients from 3 physicians who are investigators for this study. The same 3 physicians will administer the injection to their individual patients. Each of these investigators have performed a minimum of 800 injections and will be using the exact same methodology for providing the Ultrasound Guided injection. Since the injections will be performed under guidance and the approach of the injection will be identical we anticipate minimal operator effect on our study results.

An ultrasound unit will be used to identify the Glenohumeral joint with the patient in a lateral recumbent position. A posterior approach will be utilized to access the Glenohumeral space. The joint will be scanned and a marking pen will be used to mark the area of approach. The skin and probe will then be sterilized. The probe will then be replaced on the previously marked position and a 22 gauge spinal needle will be used to direct the injection into the glenohumeral space. The needle will be visualized throughout the procedure. Images will be taken of the joint before the injection, while the needle is in the joint, and post injection. They will be saved and uploaded into the medical record. Pre and post pain levels will be elicited from patient. The patient will be blinded to the study arm selected.

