8.3 Statistical methods

The primary endpoint is change from baseline of the shoulder pain and disability index (SPADI). The low dose and high dose changes will be analyzed with a two-sided two-sample t-test. Noninferiority tests with a margin of .5 will be used to test for a clinically meaningful difference between 20mg and 40mg doses and the 40mg and 80mg doses. The three groups will be summarized with descriptive statistics and univariate statistical tests using analysis of variance for normally distributed continuous variables, Kruskal-Wallis test for non-normally distributed continuous variables, and the Fisher's exact test for categorical variables. The demographic data and SPADI data will be analyzed accordingly. All statistical analyses, graphics, and reports will be prepared following best practices in conducting reproducible research in statistics utilizing various software packages built around the R software platform. [name]., Associate Professor, will serve as the Biostatistician for this study.

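### Kellgren-Lawrence grade is assessed before randomisation but used only as an entry filter; recording it and adding it as a prespecified covariate would give a modest, nearly free gain in SPADI precision

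*Combined protocol and SAP*

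**What the plan says.** KL grade appears in two places, both about eligibility. Section 3.2 lists as an exclusion "A Kellgren and Lawrence classification of 1 or less on radiograph". Section 7.2.1 explains how this is applied: once a patient is interested and meets the other criteria, "there will be one final step in assessing eligibility". The rule at that step is "The patient will be excluded if they have a Kellgren and Lawrence classification of 1 or less on radiograph". The coordinator contacts the study's musculoskeletal radiologist, and "They will then review the radiographs of the patient to make this assessment". Patients above the cut-off (grade 2, 3 or 4) can enter.

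The grade is not mentioned again:
- **Baseline data (7.2.2).** Apart from the SPADI, the items collected are these: "Patients will be asked questions regarding nicotine use, pain relievers use 24 hours prior to the injection, recent therapies for shoulder pain, and dominant arm". KL grade is not named.
- **Randomisation (7.2.2).** The text is only "The coordinator will randomize the patient", with no stratification factor.
- **Analysis (8.3).** For the 20 mg versus 80 mg contrast, "The low dose and high dose changes will be analyzed with a two-sided two-sample t-test". The non-inferiority tests (20 versus 40 mg, 40 versus 80 mg) have no stated covariates, and the remaining tests are described as univariate.

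**The concern.** The trial already arranges for a specialist to judge structural severity in every patient before allocation. Section 2.1 treats severity as relevant: "As the condition progresses, pain and functional disability increase". SPADI measures pain and disability. A baseline variable that may explain part of the outcome is therefore within reach at almost no cost, and the plan lets it go.

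Precision is at stake. Whatever variance in SPADI change the grade explains stays in the error term of every dose contrast, which widens the intervals and lowers power. There is also a practical deadline. The protocol asks only for a check against a threshold and does not say that a grade of 2, 3 or 4 is written down. If it is not, a later baseline table or adjusted analysis would need the films to be read again.

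**Working it through.** **Inputs from section 8.2.** Non-inferiority: margin 15, assumed true difference 4, SD 20, one-sided 2.5%, 80% power, 52 per group. Superiority, 20 mg versus 80 mg: difference 20, SD 40, two-sided 5%. Final size 57 per group, 171 in total. Section 8.3 gives the margin as .5, which is a separate discrepancy; the calculations here use 15.

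**Reproducing the plan's figure.** n = 2 × [SD × (1.960 + 0.842) / (margin − difference)]² = 2 × [20 × 2.802 / 11]² = 51.9, so 52 per group. This matches, and it contains no covariate.

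**Assumption.** The documents give no correlation between KL grade and SPADI change. Let R² be the share of variance that grade explains, from 0 to 10%. Adjustment multiplies the SD by √(1 − R²).

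**Power at 52 per group (normal approximation).**
- Non-inferiority: Φ(11 / (SD × √(2/52)) − 1.96)
- 20 mg versus 80 mg: Φ(20 / (SD × √(2/52)) − 1.96)

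| R² (assumed) | SD, non-inferiority | Power, non-inferiority | SD, 20 vs 80 mg | Power, 20 vs 80 mg |
|---|---|---|---|---|
| 0 | 20.0 | 80.1% | 40.0 | 72.2% |
| 1% | 19.9 | 80.5% | 39.8 | 72.7% |
| 5% | 19.5 | 82.1% | 39.0 | 74.4% |
| 10% | 19.0 | 84.0% | 37.9 | 76.7% |

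The non-inferiority sample size for 80% power falls from 52 to 50 per group at R² = 5% (unrounded 49.3) and to 47 at R² = 10% (unrounded 46.7).

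The 72% for 20 mg versus 80 mg is below the planned 80% because the 51 per group in 8.2 does not match a two-sided 5% test. That test needs 63 per group by normal approximation and 64 by t-test. This is a separate matter, but it means the contrast has little power to spare.

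**How far could chance imbalance move a SPADI contrast?** Assume 20 to 40% of patients are grade 4 and that grade 4 versus lower accounts for R² of 5 to 10%. The mean difference between the two grade groups is √R² × 20 / √(p(1 − p)), and a 10-point imbalance shifts a contrast by one tenth of it:
- smallest, p = 0.4 and R² = 5%: 0.1 × 0.224 × 20 / 0.490 = 0.9 points
- largest, p = 0.2 and R² = 10%: 0.1 × 0.316 × 20 / 0.4 = 1.6 points

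The standard error of a contrast is 20 × √(2/52) = 3.9 and the margin is 15. The shift is small beside both.

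**The case against.** The strongest reply is that this is a preference and not a defect. Randomisation makes the unadjusted tests valid, and chance imbalance in severity is already inside their error rates. That stands, and it limits the point to efficiency.

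The link between grade and outcome is also thin. Section 2.1 ties progression to the level of pain and disability, while the endpoint is change from baseline, which already subtracts level. Nothing in the documents ties KL grade to the response to an injection. That stands too: R² could be near zero, and then the SPADI gain vanishes. Grade and baseline SPADI may also overlap, so the increment over baseline SPADI may be less than the table shows. And the protocol requires only a threshold check, so the grade is not strictly already in hand. That is why recording it comes first in the fix.

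Three stronger readings are tempting and are not supported.
- **That imbalance would be mistaken for a dose effect.** With 57 per arm and an assumed grade-4 share of 20 to 40%, the highest and lowest of the three arms differ by at least 10 points with probability 40 to 54% (simulation). For any single contrast the figure is 20 to 29%. Either way it is ordinary sampling variation that the tests allow for, and its effect on SPADI is small.
- **That randomisation should be stratified by grade 2 versus 3-4.** This would not balance grade 4 against grade 3. Assuming 35% are grade 3, exact balance on that split still leaves a 31 to 46% chance of the same 10-point range in grade-4 share.
- **That the arthroplasty comparison needs adjustment for grade.** Section 1.3 lists a 1-year rate, but 8.3 defines no dedicated analysis; at most the general Fisher's exact test applies. If risk were 25% in grade 4 and 5% otherwise (assumption), the overall rate would be 9 to 13%, or about 5 to 7 events per arm (57 × 0.09 = 5.1; 57 × 0.13 = 7.4). That is too few to support much adjustment.

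**Conclusion.** The concern holds as a missed precision gain in the SPADI comparisons. The plan obtains a KL assessment before randomisation for every patient who enters, uses it only to exclude grade 1 or less, and does not carry it into the recorded data or the analysis. The planned tests remain valid without it.

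The benefit is at most modest on the range examined: 0 to 4 percentage points of power for each non-inferiority test and 0 to 4 or 5 points for 20 mg versus 80 mg, at 52 per group. This rests on an assumed R² of 0 to 10%, on the SDs in 8.2 and on the margin of 15. The increment beyond baseline SPADI is not known from the documents. The change is worth making because it costs so little and the film review is already planned, not because the analysis is unsound without it.

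**What to change.** 1. In 7.2.1, have the radiologist record the actual grade (2, 3 or 4) on the eligibility form, and carry it into the study database.
2. Report KL grade by arm in the baseline table.
3. In 8.3, replace the unadjusted SPADI comparisons with a linear model for each dose contrast, with KL grade and baseline SPADI as prespecified covariates. Take the superiority test and the non-inferiority confidence limits from the adjusted difference.

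The cost is one form field and one or two model degrees of freedom for grade (plus one for baseline SPADI). No extra film review, visit or patient is needed. The covariates should be fixed before any outcome data are examined by arm, and 10.6 plans an interim analysis after 25% of patients are enrolled. This point does not call for stratification by grade or for an adjusted arthroplasty analysis.

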7.2.2 Clinic appointment

A member of the research team will meet with the patient. The consent will be read and reviewed with the patient. After obtaining informed consent, the patient will be asked to complete the SPADI. This will be completed on paper and entered in to the REDCap database by a member of the research team. Patients will be asked questions regarding nicotine use, pain relievers use 24 hours prior to the injection, recent therapies for shoulder pain, and dominant arm. This data will be recorded in the research records. The coordinator will randomize the patient. The patient will be randomized into one of three study arms 1) 20 mg Triamcinolone with 3 cc of 1% Lidocaine, 2) 40 mg Triamcinolone with 3cc of 1% Lidocaine, or 3) 80mg Triamcinolone with 3cc of 1% Lidocaine. The injection will be prepared by a non-blinded investigator based on the study arm selected following standard of care protocols. Standard clinic protocol involves applying a patient label to the syringe. To assist with the blinding process, an additional label will be applied to the body of the syringe to ensure the volume of the syringe cannot be determined.

For the actual injection we will be using patients from 3 physicians who are investigators for this study. The same 3 physicians will administer the injection to their individual patients. Each of these investigators have performed a minimum of 800 injections and will be using the exact same methodology for providing the Ultrasound Guided injection. Since the injections will be performed under guidance and the approach of the injection will be identical we anticipate minimal operator effect on our study results.

An ultrasound unit will be used to identify the Glenohumeral joint with the patient in a lateral recumbent position. A posterior approach will be utilized to access the Glenohumeral space. The joint will be scanned and a marking pen will be used to mark the area of approach. The skin and probe will then be sterilized. The probe will then be replaced on the previously marked position and a 22 gauge spinal needle will be used to direct the injection into the glenohumeral space. The needle will be visualized throughout the procedure. Images will be taken of the joint before the injection, while the needle is in the joint, and post injection. They will be saved and uploaded into the medical record. Pre and post pain levels will be elicited from patient. The patient will be blinded to the study arm selected.

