1.2 Primary Study Endpoints

- Change in Overall SPADI scores at baseline compared to 2,4, and 6 months.
- Adverse reactions to the steroid

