7.2.3 Post-Clinic appointment

Patients will be contacted via telephone at 2 weeks to determine if any significant adverse outcomes have occurred. Patients will be contacted at 2 months, 4 months, and 6 months following the injection by email and/or phone call for completion of the SPADI and assessment of any adverse events that may have occurred as a result of the injection. Patients will also be asked what, if any, pain medications have been used in the month prior to the phone call. Patients will be given the option to complete the SPADI using the REDCap system or on paper. Patients wishing to complete the survey online will be emailed a link to access REDCap. A paper version of the survey will be mailed to the patient if that is their preferred method. A self-addressed stamped envelope will be included with the mailings. If the patient perceives that they have experienced an adverse effect the research coordinator will make a detailed record of the patient experience and the PI of the study will be contacted. .

At 12 months following the initial injection, in addition to a chart review, the patient will be contacted to determine the outcome of their shoulder pain and determine if the patient underwent any additional procedures and/or surgeries to the shoulder.

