10.3 Method of collection of safety information

Safety information will be collected by phone interview during the follow up phone calls as well as review of the electronic medical record.

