11.0 Risks

There is a risk of loss of confidentiality but precautions will be taken to prevent this from happening.

Other risks include those inherent to all steroid injections. These include pain and swelling at the site of injection, skin discoloration, increase in blood glucose, infection, and allergic reaction.

Risk of randomization

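### A blood-glucose rise is listed as a common reaction, but nothing in the plan measures it or names who could notice it, so its rate by arm will be under-detected and hard to interpret.

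*Combined protocol and SAP*

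**What the plan says.** - **Reaction expected.** Section 2.1 ends its list of the most common side effects with "cutaneous atrophy, and a transient increase in blood glucose". Section 11.0 repeats it among the study risks: "skin discoloration, increase in blood glucose, infection, and allergic reaction".
- **Endpoint.** Section 1.2 lists "Adverse reactions to the steroid" as a primary endpoint, and the hypothesis in section 1.1 expects the low dose to keep side effects down.
- **Who is enrolled.** The diagnoses excluded in section 3.2 are "Previous diagnosis of inflammatory arthritis, rotator cuff tear, or immunocompromised". Diabetes is not among them.
- **What is recorded at baseline.** Section 7.2.2 itemises "questions regarding nicotine use, pain relievers use 24 hours prior to the injection, recent therapies for shoulder pain, and dominant arm". Neither diabetes nor home glucose testing is named.
- **How reactions are found.** Section 7.2.3 limits the 2-week call to significant adverse outcomes. The contacts at 2, 4 and 6 months ask about adverse events more generally. A detailed record follows "If the patient perceives that they have experienced an adverse effect". Section 10.3 states: "Safety information will be collected by phone interview during the follow up phone calls as well as review of the electronic medical record". No glucose test is named anywhere.
- **Analysis.** Section 8.3 provides Fisher's exact test for categorical variables, with no breakdown by diabetes or by glucose testing.

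**The concern.** Patients can feel pain or swelling and can see a change in skin colour. A short-lived glucose rise generally has to be measured to be noticed. If the study does not measure it, reports will come mainly from patients who test at home, most of them probably people with diabetes. The documents do not say this; it is an inference.

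The rate observed in an arm is then the product of two unknowns: the share of patients who test, and the reaction rate among them. The plan names neither as something to record. The 2-week call is the contact closest to the injection, yet it is restricted to significant outcomes, so a modest rise may go unreported even by a patient who saw it. For this one reaction, low and similar counts across doses would be the likely result whether or not the doses differ, and a reader could take them as evidence of equal safety.

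**Working it through.** **Arm size (plan's own figure).** Section 8.2 uses a margin of 15, SD 20, assumed difference 4, one-sided 2.5% level and 80% power:

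n = 2 × (1.960 + 0.842)² × 20² / (15 − 4)² = 51.9, so 52 per group, as stated.

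For 10% loss, 52 × 1.1 = 57.2 and 52 / 0.9 = 57.8; the plan states 57. I use 57 only as the arm size.

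**Assumptions.** The documents give no diabetes prevalence, no share of home testers and no glucose reaction rate. For illustration, only testers can report a rise, and the rate among them is 25% at 20 mg and 50% at 80 mg. The share of testers, s, is varied.

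**Dilution.** Whole-arm rate = s × rate among testers. Power is the exact probability, over two binomial counts with 57 per arm, that a two-sided Fisher test gives p ≤ 0.05.

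| Share s | Testers per arm (57 × s) | Whole-arm rates, 20 vs 80 mg | Fisher power |
|---|---|---|---|
| 10% | 5.7 | 2.5% vs 5% | 2% |
| 20% | 11.4 | 5% vs 10% | 8% |
| 30% | 17.1 | 7.5% vs 15% | 15% |
| 100% (everyone can detect) | 57 | 25% vs 50% | 73% |

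The ratio of 2 between the arms survives. The absolute difference shrinks from 25 points to 5 points at s = 20%, and the power goes with it.

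**Interpretability.** A whole-arm rate of 5% is 0.20 × 25% or equally 0.10 × 50%. Without s, these cannot be told apart.

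**Does chance imbalance create false differences?** Give both arms the same rate among testers, with s from 15% to 25% and that rate from 25% to 100%. The common whole-arm rate runs from 0.15 × 25% = 3.75% to 0.25 × 100% = 25%. The false-positive rate of the two-arm Fisher test is then 0.5% to 3.1%, below 5% throughout.

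**How uneven could the arms be?** From simulated Binomial(57, s) counts of testers:

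| Share s | Two given arms: ratio ≥ 1.5 / ≥ 2 | Largest vs smallest of three: ratio ≥ 1.5 / ≥ 2 |
|---|---|---|
| 15% | 41% / 17% | 68% / 35% |
| 20% | 32% / 10% | 57% / 21% |
| 25% | 24% / 5% | 46% / 12% |

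Imbalance is common, but these are ratios of small counts of a covariate, not error rates of a conclusion.

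**What a tester-only comparison would offer.** With exactly 11 testers per arm and 25% vs 50%, Fisher power is 11%. Averaged over the random number of testers at s = 20%, it is about 16%.

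**The case against.** The strongest reply is that the randomised comparison remains sound. All patients randomised to an arm are a legitimate denominator for a reported reaction, the share of testers is balanced in expectation, and the Fisher test already allows for chance imbalance. This stands. A reader might infer that the arm rates have no valid denominator, or that a significant difference between doses could simply reflect where the patients with diabetes landed. The documents do not support either reading: the false-positive rate stays at or below 3.1% in the range checked.

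A reader might also infer that the gap cannot be repaired later. That goes too far. The chart is opened at pre-screening (sections 4.4 and 7.2.1), for safety (10.3) and at 12 months (7.2.3), and the linking list is kept until study completion (6.2.2), so diabetes status could be retrieved before then. Section 7.2.2 lists questions put to the patient, not necessarily the whole dataset. Section 8.3 mentions demographic data without itemising them, and section 10.2 says overall health will be reviewed. The accurate statement is that diabetes is not named as a recorded item. What the chart may not supply afterwards is whether a patient was testing at home and saw a rise after the injection.

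Nor do the documents say that the glucose rise depends on dose. They hypothesise fewer side effects at the low dose in general. Finally, glucose is one of seven reactions in section 2.1's list of common side effects, so the point does not reach the rest of the endpoint.

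**Conclusion.** The point holds as a weakness in ascertainment for one named reaction. As written, the plan is likely to under-detect glucose rises and to yield an arm rate that cannot be interpreted without the share of patients able to notice one. Under the assumed 20% share and 25% vs 50% among testers, a 25-point difference appears as a 5-point difference with about 8% power; for shares of 10% to 30%, power is 2% to 15%. The practical risk is a reassuring null result that carries little information.

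This rests on one inference (mainly home testers can report a rise) and on assumed shares and rates. It is not a claim of bias, of inflated error or of an invalid denominator, and it does not affect the SPADI analysis or the other reactions.

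**What to change.** 1. Add two yes/no baseline fields: diabetes status, taken from the chart review already done at pre-screening, and home glucose testing, from the same review or, where the chart is silent, asked with the section 7.2.2 questions.
2. At the existing 2-week call, ask patients who test whether their readings rose after the injection, in the same words in all three arms.
3. State in section 8.3 that glucose reactions will be reported by arm descriptively, both among patients who test and among all randomised patients, with the number of testers per arm shown.
4. State that similar glucose counts across arms will not be presented as evidence of equal safety.

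The cost is one or two fields, one question at an existing contact and an extra table row; there is no new visit or procedure. The limit is that about 11 testers per arm (at an assumed 20%) cannot support a powered comparison, and patients who do not test remain unmeasured. The gain is better detection and a rate that can be interpreted.
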